7.0 CLINICAL TRIAL SUPPLIES

7.1 Test and Non-Test Articles

The active test article, L1-79 and matching placebo will be supplied to the Investigator as capsules in sealed bottles of 100 capsules of L1-79 or matching placebo. The study pharmacist will allocate the appropriate number of active or placebo into secondary packaging for distribution to subjects.

Each dose will consist of 2 capsules. Doses for subjects in the 100 mg group will be comprised of one 100 mg capsule and 1 placebo capsules while those in the 200 mg group will consist of two 100 mg capsules for each dose.

A drug log will be maintained by the Investigator and all dispensed medications as well as unused medications and those returned by subjects or their caregivers will be logged out and logged in. Empty drug containers will not be returned, but those containing medication will be returned at visits for study weeks 2 and 4 and will be counted, logged in, and stored by the Investigator until the end of the study.

7.2 Preparation of the Study Drugs

The study pharmacist will prepare drugs for dispensing to the subjects to take home. Bottles of 100 capsules will be provided for placebo and 100 mg of L1-79. The pharmacist will package the study medications as individual doses at the study site in the following manner:

7.2.1 ASSIGNED DOSAGE PATIENTS

- At each site, the pharmacist will prepare 44 individual doses (3 doses/d x 14 days + 2 extra doses) with each dose in an individually labeled envelope for six patients (to allow for 1 drop out) in each dosage group. Although not all 5Assigned Dosage Patients in a dosage group will be treated at each site there will be sufficient drug to accommodate all of these patients if one site can enroll faster than another.
- For 2 weeks of daily dosing, each patient would receive $3 \times 14 = 42 + 2$ extra doses for a total of 44 doses, each dose will be individually packaged in envelopes. The envelopes will be placed in a cardboard box
- Since 2 weeks is the limit for how much drug the FDA guidelines will allow study materials to be packaged in this manner, this process would have to be repeated twice at each study site

7.2.2 RANDOMIZED PATIENTS

- The pharmacist will place individual doses comprised of 2 capsules each in individual envelopes for 12 subjects (to allow for 2 dropouts) in 3 different treatment groups in the following manner:

- Each dose is comprised of 2 capsules to maintain a double-blind. They are distributed as:
 - Placebo group: 2 placebo capsules
 - 100 mg group: 1 x 100 mg capsule and 1 x placebo
 - 200 mg group: 2 x 100 mg capsule
- For 2 weeks of daily dosing, each patient would receive $3 \times 14 = 42 + 2$ extra doses for a total of 44 doses, each dose will be individually packaged in envelopes. The envelopes will be placed in a cardboard box
- Since 2 weeks is the limit for how much drug the FDA guidelines will allow study materials to be packaged in this manner, this process would have to be repeated twice at each study site.
- Because of the double-blind nature of the trial, each box is labeled with a sticker that has the study number and patient study number which derives from a random code that links study numbers with dosage groups.

7.3 Dispensing the Study Drug

Study drug will be dispensed as a two week supply during study weeks 0 and 2 visits.. Drugs will be allocated to subjects on a randomized and double-blinded basis. Two containers of 42 doses will consist of the study drug for each patient. Each container will be labeled with the patient's study number.

At the accession visit prior to week 1 and at the post week 2 visit each patient will receive a container of drug corresponding to their study number. Neither the Investigator or the sponsor will know to which dosage group any patient is assigned.

7.4 Labeling of Test Articles

Each drug container will contain 2 weeks of study drug and two extra doses to be used in the event a dose or two is lost, and will be labeled as follows,

- Protocol number
- Storage requirements
- Investigational use statement "Experimental Clinical Use Only"

Each dose consisting of 2 capsules will be individually wrapped and provided within the larger container will be labeled as follows:

Envelope Labels

Protocol HT 02-121 Investigational Drug--Limited by Federal Law to investigational Use
 
Patient No. XX-YYY
 
Store at room temperature
 
Contents: 1 individual dose comprised of 2 capsules each
 
Take 1 dose of 2 capsules by mouth at upon arising, at 4:00 PM and at bed time. Take with 8 oz. of water.
 
Batch #: XXXX
 
Keep out of Reach of Children

Each individual dose will be labeled as follows:

Side of Box

Protocol HT 02-121 Investigational Drug--Limited by Federal Law to investigational Use
 
Store at room temperature
 
Take 1 package of 2 capsules by mouth at upon arising, 1 capsule at 4:00 PM and one capsule at bed time. Take with 8 oz. of water.
 
Keep out of Reach of Children

--

Top of Box

Patient No: XX-YYY
 
Study HT 02-121
 
Box 1 [or 2]
 
Keep out of Reach of Children

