APPENDIX E: SAMPLE COLLECTION METHODS.....		58
APPENDIX F: DSM-5 DIAGNOSTIC CRITERIA FOR AUTISM SPECTRUM DISORDER		59

RESTRICTED DISTRIBUTION OF PROTOCOLS

- This protocol contains information that is confidential and proprietary. The information contained herein is provided for the purpose of conducting a clinical trial in collaboration with [name].
-
- The contents of this protocol may be disclosed to study personnel under your supervision and to your Institutional Review Board(s). The contents of this protocol may not be disclosed to any other parties (unless such disclosure is requested by [name]).

PROTOCOL SYNOPSIS

- Study Drug: L1-79
- Protocol Number: HT 02-121

Protocol Title: A Phase 2 Safety Study of L1-79 in the Treatment of Autism

- Study Phase: 2
- **Study Design:** This study has a dose escalating cohort design. Treatment arms consist of L1-79 at doses of 100 mg t.i.d (or placebo), or 200 mg t.i.d., (or placebo). Pharmacokinetics will be assessed in initial cohorts of 5 patients for each dose group followed by a double blinded, placebo-controlled assessment of PK/PD and safety in a cohort of 15 patients randomized 2:1 active to placebo. Groups 1& 2 below can start simultaneously. While the FDA is reviewing the data from Group 1, Groups 2 and the placebo patients randomized with Group 2 will be ongoing. All 5 subjects assigned to Group 1 (100 mg L1-79) must have completed the PK portion of the study with results analyzed and accepted by the FDA before subjects in Groups 3-5 can begin treatment.
- Sample Size: N=40
 - Group 1 (n=5) 100 mg L1-79 (1x100mg capsule+1 placebo capsule)
 - Group 2 (n=10) 100mg L1-79 (1x100mg capsule+1 placebo capsule)
 - Group 3 (n=5) 200 mg L1-79 (2x100 mg capsules)
 - Group 4 (n=10) 200 mg L1-79 (2x100 mg capsules)
 - Group 5 (n=10) Placebo (2 placebo capsules)

All Groups will receive the assigned study drug three-times daily.

- **Study Population:** Male subjects with autism between the ages of 13 and 21 years of age who meet the entry criteria and who are able to complete standardized measures allowing them to participate in this study.

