5.0 STUDY PROCEDURES

5.1 Consent and Assignment of Subjects to Treatment

Each patient or their representative must sign a copy of the informed consent document. The patient will be asked to provide assent to participate in the study ([Appendix B](#)). The study staff will explain this form in non-technical language, in detail, and will answer all questions that a patient might ask. Staff will explain to all subjects that subjects who qualify for entry into this trial will receive an experimental treatment which they must take daily as instructed and must come back to the clinic for regularly scheduled visits.

The patient, or caregiver of each patient will sign the Study Compliance Agreement ([Appendix D](#)) in which they agree to administer the test medication as instructed by their attending physician in compliance with this protocol. Further, this agreement stipulates that the caregiver of each patient will complete their obligations under this protocol as instructed by the Investigator and his/her staff; including visit attendance, test form completion, reporting of adverse events, and so forth. Additionally, this agreement requests, but does not require, that caregivers provide any *ad hoc* comments regarding the behavior of the patient or their responses to treatment be forwarded weekly to the Investigator to document changes in the patient's condition at home and to add any notes to the database that are appropriate to understanding the response of the patient to treatment.

After satisfying entry criteria and giving signed informed consent and agree to the compliance document, subjects will be enrolled in the trial

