5.2 Drug Administration

5.2.1 THE L1-79 REGIMEN

Subjects will receive either 100 mg or 200 mg or matching placebo t.i.d. for a total of 28 days of dosing. The doses of L1-79 were determined based upon preliminary clinical research in subjects between 2½ and 24 years of age and doses between 90 and 200 mg t.i.d..

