5.2.3 DOSING INSTRUCTIONS

The study medication will be dispensed in containers that contain sufficient study drug for two weeks of t.i.d. dosing, plus 2 additional doses to be used if needed (44 doses) at the Day 0 and Week 2 visits. In order to maintain the double-blind, each dose will be

comprised of 2 capsules as described below. Thus, each biweekly drug allotment will consist of 44 packages of 2 capsules each sufficient for 3 daily doses times 14 days plus 2 extra doses to be used in the event that a dose or two is lost. Subjects will be instructed to take a dose (2 capsules) in the morning upon arising, afternoon at approximately 4 pm, and just prior to bed time. Capsules can be taken orally, or their contents can be mixed with food or drink as deemed necessary by the caregiver to facilitate the administration of the medication. Care will be taken to assure that 8 oz of water are given at the time of dosing to maintain hydration. For subjects unable to swallow capsules the may take the drug in food or drink. Patients should also be cautioned about potential sedative effects and instructed not to conduct activities like driving, which require alertness.

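### The side-of-box label directs 4 capsules a day; the envelope label, the dosing section and the supply all require 6

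*Combined protocol and SAP*

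**What the plan says.** Section 7.4 gives the text of both labels.

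- Side of box: "Take 1 package of 2 capsules by mouth at upon arising, 1 capsule at 4:00 PM and one capsule at bed time".
- Envelope: "Take 1 dose of 2 capsules by mouth at upon arising, at 4:00 PM and at bed time", with the contents given as "Contents: 1 individual dose comprised of 2 capsules each".

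The rest of the protocol describes one regimen.

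- Section 5.2.3 has subjects instructed to "take a dose (2 capsules) in the morning upon arising, afternoon at approximately 4 pm, and just prior to bed time". On supply it says that "each biweekly drug allotment will consist of 44 packages of 2 capsules each sufficient for 3 daily doses times 14 days", plus 2 spare doses.
- The synopsis says "All Groups will receive the assigned study drug three-times daily", and Section 5.2.1 says "Subjects will receive either 100 mg or 200 mg or matching placebo t.i.d. for a total of 28 days of dosing".
- Section 7.1 sets every dose at 2 capsules. Sections 7.1 and 7.2.2 give the make-up: one 100 mg capsule and one placebo capsule in the 100 mg group, two 100 mg capsules in the 200 mg group, and two placebo capsules in the placebo group.
- Under Section 5.1 the patient or caregiver agrees to "administer the test medication as instructed by their attending physician in compliance with this protocol".

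**The concern.** The box and the envelope cannot both be followed. The box line separates a package of 2 capsules in the morning from a single capsule at each of the two later times, and it states the single capsule twice. A caregiver who reads it literally will underdose.

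The 100 mg arm has a further problem. Each envelope holds one active and one placebo capsule, and Section 5.2.2 describes the placebo as matched in appearance. Once single capsules are taken, nobody can tell whether a given afternoon or bedtime dose contained drug.

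Timing matters too. Escalation to 200 mg depends on FDA review of first-week safety and PK data from the 5 lead-in patients at 100 mg (Sections 4.3, 5.1.1 and 5.9.3.3). Unused medicine is first counted at week 2 (Sections 5.9.2.4 and 7.1). The week 1 visit lists confirmation of medication administration (Section 5.9.2.3), but no method is given. Underdosing in week 1 could therefore reach the escalation report before any count shows it. One misdosed patient would be one fifth of that group.

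**Working it through.** **Inputs.** 2 capsules per dose (7.1); three dosing times (5.2.1, 5.2.3); 44 packages per two weeks (5.2.3, 7.2.1, 7.2.2); active capsule strength 100 mg; make-up by arm as in 7.1 and 7.2.2; the two label texts in 7.4.

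**The plan's own supply figure.** 3 doses × 14 days + 2 spare = 44 doses, as stated. 44 × 2 = 88 capsules.

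**Capsules per day.** Envelope and 5.2.3: 3 × 2 = 6. Side of box: 2 + 1 + 1 = 4. Shortfall: (6 − 4)/6 = 33%.

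**Cross-check from Section 5.3.** The highest dose is said to equal 300 mg of Demser daily, and L1-79 is stated to contain 50% of the active Demser ingredient. 300/0.5 = 600 mg/day, which is six 100 mg capsules. This also fits 6 and not 4.

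**Daily dose if the box is followed**

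| Arm | Planned | Box followed | Change |
|---|---|---|---|
| 200 mg | 6 × 100 = 600 mg | 4 × 100 = 400 mg | −33% |
| 100 mg, one envelope split between 4 PM and bedtime | 3 × 100 = 300 mg | 100 + (100 + 0) = 200 mg | −33% |
| 100 mg, single capsules from separate envelopes | 300 mg | 100 + (0 to 200) = 100 to 300 mg | 0 to −67% |
| Placebo | 0 | 0 | none |

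The morning dose is the same under both labels.

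**First 7 days.** 7 × 4 = 28 capsules against 7 × 6 = 42. In the 100 mg lead-in group the planned total is 7 × 300 = 2100 mg. The split-envelope route gives 7 × 200 = 1400 mg. The separate-envelope route gives between 7 × 100 = 700 mg and 7 × 300 = 2100 mg; these are outer bounds.

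**Supply and returns over 14 adherent days.** At 6 a day, 84 capsules are used and 88 − 84 = 4 come back (the 2 spare doses). At 4 a day, 56 are used and 88 − 56 = 32 come back, and 88 capsules would last 88/4 = 22 days. The 32 holds by either route:

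- Split: 2 × 14 = 28 packages opened, 16 unopened, 32 capsules.
- Separate: 3 × 14 = 42 packages opened, leaving 28 loose capsules plus 2 unopened packages (4), 32 capsules.

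Section 7.3 gives 42 doses per container instead of 44. With 42 doses the returns are 28 against 0, so the difference is 28 capsules either way.

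**The case against.** The strongest reply is that this is a slip, capsule written for package, and that the packaging works against the error.

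- Each dose sits in its own envelope, which carries the correct direction and must be opened every time. To follow the box, a caregiver has to remove one capsule and set the other aside, against the label in hand.
- Caregivers are instructed in person (5.2.3) and have their responsibilities explained in detail (5.9.1.2).
- The first dose is given at the site (5.2.3.1), and the week 1 check may catch a mistake.
- The error runs toward underdosing. No day on the box schedule exceeds the planned daily dose, so what is at risk is the validity of the data, with no overdose.
- PK blood is drawn 1 hour after dosing (5.1.2). If the dose before a weekly sample is the morning dose, it is complete under both labels. The documents give no visit times, so this is an assumption.
- The bounds of 700 and 2100 mg need all 14 single capsules of the week to be of one kind. If each pick were random (also an assumption), each bound would have probability (1/2)^14 = 1/16,384. The mean would be 700 + 14 × 0.5 × 100 = 1400 mg, as with a split envelope.

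All of this stands as a limit on likelihood and size. The second FDA report on the lead-in patients also follows both capsule counts, so it is better protected than the first. None of it makes the printed direction right. Even with a complete dose before sampling, carry-over from earlier doses, the 24-hour urine and first-week safety exposure could be reduced.

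**Conclusion.** The concern holds. The box label is wrong as written: 4 capsules a day against 6, one third fewer. The intended regimen is not in doubt, because every other relevant statement gives 6.

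The consequence is conditional on a caregiver following the box. It would then be 400 instead of 600 mg/day at 200 mg. At 100 mg it would be 200 instead of 300 mg/day with a split envelope, or an unknowable 100 to 300 mg/day with separate envelopes. The placebo arm loses no active drug. The documents give no basis for estimating how many families would be affected, so no bias in any arm is claimed.

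Correction is required because this is an operative dosing direction to patients in a trial whose primary objective is safety at two specified dose levels. The rating does not rest on a predicted rate of misdosing.

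**What to change.** Before boxes are printed or dispensed, replace the side-of-box direction with: *One package (2 capsules) by mouth on arising, one package (2 capsules) at 4:00 PM, and one package (2 capsules) at bedtime.* Repeating the envelope direction on the box, or removing the direction from the box, would also end the conflict. The corrected label gives 6 capsules a day, 84 in 14 days, with the 2 spare doses left from 88. The cost is one line of label text, and no new procedure is needed.

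Only if boxes with the present text have already been issued: tell caregivers the correct regimen at once and reprint. Use the week 2 and week 4 counts, which are already scheduled, to identify and report patients who took fewer capsules than planned. About 32 capsules returned after 14 days, where 4 are expected, is the pattern to look for.

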7.5 Storage of Test Article

L1-79 will be stored in a locked and secure cabinet at room temperature. Study drug will be logged out upon dispensing and unused study drug will be returned to the study site and logged in.

7.6 Accountability of Test Article

A dispensing record of test preparations must be maintained by the study site to assure accountability of all medications supplied and administered. The dispensing log must include:

- Amount of study drug dispensed
- Date drug received
- Investigator's signature
- Physical inventory prior to dispensing
- Physical inventory after dispensing

The dispensing record with drug inventory will be reviewed at each monitoring visit.

The L1-79 and placebo supplied for this study is only for use in subjects properly consented and enrolled under this protocol. These drugs must be kept physically separate from standard clinic or office drug supplies.

Unused investigational material will be accounted in the drug log disposed appropriately by the Investigator.

8.0 ADMINISTRATIVE

8.1 Serious Adverse Experience Reporting

A serious adverse experience is defined as any event that results in one of the following outcomes:

- death;
- any life-threatening condition;
- persistent or significant disability/incapacity;
- requires or prolongs inpatient hospitalization;
- a congenital anomaly or birth defect in an offspring of a patient exposed to L1-79 or
- On the basis of appropriate medical judgment, the experience may jeopardize the patient and may require medical or surgical intervention to prevent one of the aforementioned outcomes.

Any serious adverse experience must be reported within 24 hours by entering the information into the appropriate screen in the online data reporting system. This will generate automatic emails to alert the Sponsor and the study monitor contact listed below

After the initial reporting of the experience the following documentation must be entered into the electronic data collection system in the appropriate screen within 5 working days.

- The serious adverse experience form; and
- Any additional documentation (e.g., autopsy report, hospital records, and/or laboratory tests) required to support or add information to the serious adverse experience form. Any such information will be scanned and entered in to the eCRF system to be kept with the patient's records.

All serious adverse experiences must be reported by the Investigator to their IRB in writing, as well as the study sponsor.

8.1.1 NON-SERIOUS ADVERSE EXPERIENCE REPORTING

Non-serious adverse experiences will be reported on the appropriate electronic case report form (eCRF) as described in Section 5.11. The Sponsor is responsible for the reporting of non-serious adverse experiences to the FDA in the IND annual report.

8.2 Electronic Data Collection

Data will be collected via EDC. All data is to be entered within 3 days after each patient evaluation. Data that requires transcription will be transcribed within 3 days.

All entries into the database must be supported by original source documentation (e.g., laboratory reports) maintained at the investigational site.

Correction(s) of data in the database may only be made in a manner that indicates the error and leaves the previous entry identifiable by entering the correct values next to those marked as incorrect. An audit trail will be generated automatically as the data capture system will note the person making a change, the date of the change, and the original information will be maintained as well as the corrected information.

The Investigator is required to review all entries into the database and electronically sign where indicated to attest to the accuracy of the data recorded on the form.

8.3 Investigator Requirements

8.3.1 PRIOR TO STUDY INITIATION

Prior to study initiation, the Investigator will complete and forward the following essential documentation:

- Any and all forms required by local regulatory authorities plus current curriculum vitae for each individual named on the form and/or any other forms required by local regulatory agencies.
- A signed and dated Investigator Agreement Page (Section 10 of the protocol).
- Identification of the clinical laboratory facilities that will be used including certification or proficiency ratings and normal ranges for the determinations described by the protocol and a copy of the curriculum vitae for the lab director. This information will be forwarded to the Data Management group so that the normals are entered into the data management system, and the laboratory documentation scanned and kept within the site information. Any changes in laboratory normals or certifications will be collected and handled in the same manner.
- A copy of the formal written notification of approval of the protocol and consent form to the Investigator from the IRB, in compliance with FDA regulations (The written notification of “Action” is to be signed by the chairman or any persons authorized in the IRB’s SOPs).
- A list of institutional review board members and their respective titles, occupations, and institutional affiliations or provide a general assurances number for the IRB.

- An actual copy of the IRB-approved informed consent form and other adjunctive materials to be used in this study to elicit and record patient consent in compliance with Food and Drug Administration (FDA) regulations.
- Documentation to assure local and state regulations has been met, if applicable.

8.3.2 INFORMED CONSENT

The informed consent should be obtained by means of a standard written statement. It should be written to be easily understood by the patient or legal guardian. All aspects of this study including objectives, methods, schedules and so forth should be explained in easy to understand terms, and questions should be elicited and answered in full in order to enable a truly informed consent. The patient/legal guardian should be given the time to read and understand the statement and be afforded the opportunity to ask questions before signing his/her consent and dating the document. The patient/legal guardian should receive a copy of the written statement once she and the Investigator have signed the informed consent.

The informed consent form must be considered as a part of the protocol. It is to be submitted by the Investigator along with the protocol for approval to the IRB.

No study procedures will be initiated prior to obtaining a valid, signed, informed consent.

The informed consent form is presented in [Appendix C](#).

